6.2.5. Vital Signs & Weight

Vital signs including blood pressure, heart rate, respiratory rate, and oral temperature will be measured by the investigator or qualified designee as per standard institutional guidelines at each study visit as indicated in [Appendix 2](#). Weight will be collected at the same visits vital signs are taken.

6.2.6. Electrocardiogram Assessment

A single 12-lead electrocardiogram (ECG) will be collected at Screening, Day 1, and every 4 weeks thereafter at subsequent visits, and at the EOT and EOS visits, as indicated in [Appendix 2](#). The investigator will review all ECGs and retain the tracing with the source documents.

6.2.7. Performance Status

Performance status will be scored using the ECOG performance status scale index (refer to [Appendix 3](#)), at Screening, Day 1 and every 4 weeks thereafter, EOT, EOS, and 30-day Safety Follow-up visits. ECOG used to determine eligibility must be the performance status during the screening period. ECOG performance status on Day 1 may be waived if it was conducted during screening within 4 days of Day 1.

6.2.8. Laboratory Assessments

The central laboratory will be responsible for chemistry, hematology, coagulation, urinalysis, and serum pregnancy testing (per [Table 6-1](#)) as well as processing and/or storage of other study samples. Specific instructions for processing, labeling, and shipping samples will be provided in a central laboratory manual. The date and time of sample collection will be reported to the central laboratory.

If central laboratory results are not available, local laboratories may be used for dosing decisions. Local laboratory assessments resulting in a dose change or as part of an AE assessment, which is not supported by central lab results, will be reported on the eCRF.

Urine pregnancy test will be performed locally at the site.

Table 6-1. Analytes

Chemistry	Urinalysis	Hematology	Other
Albumin	Color and appearance	WBC	Serum β -hCG or urine pregnancy test ^c Thyroid Function Tests (TSH, T3, freeT4) ^d
Alkaline phosphatase	Specific gravity	Hemoglobin	
ALT	pH	Hematocrit	
AST	Occult blood	Platelet	
Bicarbonate	Protein	ANC	
BUN	Glucose		
Calcium	Bilirubin	Differential	
Chloride	Leukocyte esterase	Eosinophils	
Creatinine ^a	Nitrite	Lymphocytes	
Glucose	Urobilinogen	Monocytes	
Lipase	Ketones	Neutrophils	
Amylase	Microscopic ^b		
Magnesium		Coagulation	
Phosphorus		PT/INR	
Potassium		aPTT	
Sodium			
Total bilirubin			
Direct bilirubin			
Total protein			
CEA			
CA125			

ANC = absolute neutrophil count; ALT = alanine aminotransferase; aPTT = Activated Partial Thromboplastin Time; AST = aspartate aminotransferase; BUN = blood urea nitrogen; CEA=carcinoembryonic antigen; β -hCG = beta-human chorionic gonadotropin; INR = International Normalized Ratio; PT = Prothrombin Time; WBC = white blood cell; CA125 = Carbohydrate Antigen 125; TSH = thyroid stimulating hormone; T3 = triiodothyronine; Free T4 = free thyroxine

a Estimated creatinine clearance (CL_{cr})/glomerular filtration rate will be calculated based on the Cockcroft-Gault formula using actual body weight: $CL_{cr} \text{ (mL/min)} = (140 - \text{age [years]}) * \text{weight (kg)} / (\text{serum creatinine [mg/dL]} * 72)$. If the subject is female, multiply the quantity by 0.85.

b Reflex testing based on other abnormalities

c Females of child-bearing potential only. Serum pregnancy will be conducted at Screening. Urine pregnancy will be conducted pre-dose on Day 1, every 4 weeks thereafter, at EOT, and EOS, 30-day, and 5-month Safety Follow-up

d TSH, T3, and free T4 will be tested by the central laboratory at screening. From Week 8 and beyond, T3 and T4 will be tested reflexively based on abnormal TSH results.

Screening laboratory samples should be obtained within 28 days prior to randomization. Blood samples will be obtained for hematology, chemistry, coagulation, thyroid function, and pregnancy testing for female subjects. A urine sample will also be obtained at screening for urinalysis.

Blood samples for hematology and chemistry will be obtained at pre-dose on Day 1 and every 2 weeks thereafter, EOT, EOS, 30-day, and 5-month Safety Follow-up. Blood samples for Thyroid Function Tests (TSH, T3, free T4) will be collected every 8 weeks, and at EOT, EOS, 30-day, and 5-month Safety Follow-up. A urine sample for urinalysis and pregnancy testing for female subjects will also be obtained on Day 1 and every 4 weeks thereafter, EOT, EOS, 30-day, and 5-month Safety Follow-up. Blood samples for coagulation will be obtained at EOT and EOS.

At any time during the study, abnormal laboratory parameters that are clinically relevant (eg, lead to clinical symptoms or signs, require therapeutic intervention), and constitute an AE must be recorded in the eCRF.

6.2.8.1. Pregnancy Test

All females of childbearing potential (see [Appendix 4](#)) will have a serum pregnancy test at screening. Urine pregnancy tests will be performed every 4 weeks starting on Day 1, EOT, EOS, 30-day, and 5-month Safety Follow-up.

6.2.8.2. Pretreatment, On-treatment and Progression Biopsies

- If biopsies are endoscopic gastric, at least 4 biopsies at each time-point (pre-treatment, on-treatment, and at progression) should be obtained. If biopsies are from other sites, core needle biopsies, excisional, resections, incisional, or punch biopsies are acceptable. For core needle biopsies, at least 3 cores should be collected. Refer to the laboratory manual for tissue processing instructions. It is preferred that on treatment and progression biopsies be taken from primary (gastric or GEJ tissue) lesions and/or the same site as the pre-treatment (or archival) tissue. If tissue is not available or accessible from the primary lesion (gastric or GEJ tissue), biopsies of metastatic lesions are acceptable. Pre-treatment: To be obtained within the screening window or any time after last line of therapy; The pretreatment biopsy is requested if archival tumor sample provided to meet Inclusion Criterion #6 is from before the last line of therapy
- On-treatment: To be obtained anytime within the window of Week 5 through Week 9
- At progression: To be obtained at disease progression (if medically feasible)

6.2.8.3. Anti-Andecaliximab Antibody

For Arm A only, blood samples for anti-andecaliximab antibody will be collected prior to dosing at the following visits: Day 1, Weeks 4, 8, 16, 24, and every 3 months thereafter, and at the EOT and EOS visits.

6.2.8.4. Andecaliximab Pharmacokinetics

For Arm A only, blood plasma samples will be collected for andecaliximab PK at 30 (\pm 15) minutes after the end of infusion on Day 1, prior to dosing, and 30 (\pm 15) minutes after the end of infusion at Weeks 4, 8, 16, 24, and every 3 months thereafter, and at the EOT and EOS visits.

6.2.8.5. Biomarkers

Samples for biomarker analysis as listed in [Table 3-1](#) will be collected as follows and in [Appendix 2](#):

- Blood biomarker samples will be collected at screening, prior to dosing on Day 1, Weeks 2, 4, 8, 16, 24, and every 3 months thereafter, and at EOS or at disease progression.
- An oral sample (saliva or other) for characterization of oral microbiome diversity will be collected prior to dosing on Day 1.

6.2.9. Disease and Response Assessment

6.2.9.1. Efficacy Measurement

RECIST version 1.1 [{Eisenhauer 2009}](#) [[Appendix 5](#)] will be used for assessment of tumor responses for the purposes of study evaluation, managing patients on protocol treatment, and decision making for discontinuation of study therapy due to disease progression, with some modifications to account for atypical responses which may occur with immune-based therapies [{Swaika 2015}](#). Given that anti PD-1 agents produce antitumor effects by potentiating endogenous cancer-specific immune responses, the response patterns seen with these agents may extend beyond the typical time course of responses seen with cytotoxic agents. In addition, anti-PD-1 therapies can occasionally manifest a clinical response after an initial increase in tumor burden or even the appearance of new lesions (“tumor flare” or “pseudoprogression”) [{Topalian 2014}](#). In these cases, standard RECIST may not provide an accurate response assessment of anti PD-1 agents.

Therefore, RECIST 1.1 will be used [[Appendix 5](#)] with the following adaptations:

If imaging shows a CR or PR, tumor imaging should be repeated at least 4 weeks (≥ 4 weeks) later to confirm response, per RECIST 1.1 guidelines. Subjects will then return to regular scheduled imaging every 8 weeks starting with the next protocol-specified imaging time-point. Subjects who obtain a confirmatory scan do not need to undergo scheduled imaging assessment ≤ 2 weeks later (eg, if a subject obtains a scan at Week 22 to confirm a Week 16 response, they will not also be required to complete the scheduled Week 24 scan).

If imaging shows progressive disease (PD), it is at the discretion of the investigator to keep the subject on study treatment or to stop study treatment until imaging is repeated ≥ 4 weeks later in order to confirm PD (adapted from the immune-related response criteria recommendations) [{Wolchok 2009}](#). Patients that are deemed clinically unstable or who have biopsy-proven new metastatic lesions are not required to have repeat imaging for confirmation. The decision to continue a subject on study while awaiting PD confirmation will be based on clinical judgment of a subject’s overall clinical condition, including performance status, clinical symptoms, and laboratory data.

At a minimum, subjects must meet the following criteria for continued treatment on study after disease progression is identified at a tumor assessment:

- Absence of signs and symptoms (including worsening laboratory values) indicating disease progression
- No decline in ECOG performance status
- Absence of rapid progression of disease or of progressive disease at critical anatomical sites (eg, cord compression) requiring urgent alternative medical intervention

Study treatment may continue under the following circumstances after repeat/confirmatory imaging (≥ 4 weeks after initial scan showing PD):

- If repeat imaging shows $< 20\%$ tumor burden increase compared to nadir, stable or improved previous new lesion (if identified as cause for initial PD), and stable/improved non-target disease (if identified as cause for initial PD), treatment may be continued and/or resumed (PD is not confirmed).
- If repeat imaging confirms PD due to any of the scenarios listed below, subjects will be discontinued from study therapy with the following exception: if the subject is achieving a clinically meaningful benefit, and there is no further increase in the tumor burden at the confirmatory tumor imaging compared to the initial PD assessment, an exception to continue treatment may be considered following consultation with the Sponsor. In this case, if treatment is continued, tumor imaging should continue to be performed at the protocol specified intervals.

In determining whether or not the tumor burden has increased or decreased, site study team should consider all target lesions as well as non-target lesions.

If repeat imaging shows an objective response or stable disease relative to nadir, treatment with study medication may continue and subjects will return to regular scheduled imaging every 8 weeks starting with the next protocol-specified imaging time-point. Subjects who obtain a confirmatory scan do not need to undergo scheduled imaging assessment ≤ 2 weeks later (eg, if a subject obtains a scan at Week 14 to confirm a Week 8 PD and progression is not confirmed, they will not also be required to complete the scheduled Week 16 scan).

Progressive Disease is confirmed at repeat imaging if:

- Tumor burden remains $\geq 20\%$ (and at least 5 mm absolute increase) compared to nadir
- Non-target disease resulting in initial PD is worse (qualitative)
- New lesion(s) resulting in initial PD is worse (qualitative)
- Additional new lesion(s) since last evaluation

If repeat imaging confirms PD, subjects will be discontinued from study therapy.

Table 6-2. Imaging and Treatment after First Radiologic Evidence of Progressive Disease

	Clinically Stable		Clinically Unstable	
	Imaging	Treatment	Imaging	Treatment
First radiologic evidence of PD by RECIST 1.1	Repeat imaging at ≥ 4 weeks at site to confirm PD	May continue study treatment at the local site Investigator's discretion while awaiting confirmatory tumor imaging by site by irRECIST.	Repeat imaging at ≥ 4 weeks to confirm PD per physician discretion only	Discontinue treatment
Repeat tumor imaging confirms PD by RECIST (see modifications in protocol)	No additional imaging required	Discontinue treatment (exception is possible upon consultation with sponsor)	No additional imaging required	N/A
Repeat tumor imaging shows SD, PR, or CR by RECIST (see protocol for details)	Continue regularly scheduled imaging assessments	Continue study treatment at the local site Investigator's discretion	Continue regularly scheduled imaging assessments	May restart study treatment if condition has improved and/or clinically stable per Investigator's discretion. Next tumor image should occur according to the every 8 week imaging schedule

In subjects who discontinue study therapy early without documented disease progression, every effort should be made to continue monitoring their disease status by radiologic imaging following guidelines for end of study follow-up (Section 6.2.9.2).

When feasible, subjects should not be discontinued until progression is confirmed; investigators should discuss with the Gilead Medical Monitor prior to subject discontinuation.

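### Protocol 6.2.9.1: the rule for unconfirmed PD sets no condition on additional new lesions, although the confirmed-PD list in the same section makes one sufficient

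*Protocol*

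**What the plan says.** After a first radiologic PD, Protocol 6.2.9.1 asks for a repeat scan at least 4 weeks later and gives two sets of rules for reading it.

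The first continuation bullet has three conditions: burden less than 20% above nadir; a "stable or improved previous new lesion (if identified as cause for initial PD"; and non-target disease that is stable or better, again only if it caused the first PD. When they are met, "treatment may be continued and/or resumed (PD is not confirmed".

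The second bullet covers a repeat scan that confirms PD under any item of the list that follows: "subjects will be discontinued from study therapy with the following exception". The exception needs a clinically meaningful benefit to the subject and that "there is no further increase in the tumor burden at the confirmatory tumor imaging compared to the initial PD assessment". Then "an exception to continue treatment may be considered following consultation with the Sponsor".

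The list of findings that confirm PD has four items. The last is "Additional new lesion(s) since last evaluation". The section closes by repeating that subjects with confirmed PD stop study therapy.

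**The concern.** The two sets of rules should sort every repeat scan into one class or the other. The bullet looks only at the new lesion that caused the first PD, while the list also looks for lesions that have appeared since. One scan can therefore be unconfirmed PD under the bullet and confirmed PD under the list.

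At stake is the working rule for treating beyond first progression in an open-label trial. A site that relies on the bullet could keep treating without showing clinical benefit, without checking for a further increase since the first PD scan, and without consulting the Sponsor. Imaging also depends on the classification, because Protocol 6.2.9.2 continues scans until the site's initial PD is confirmed, unless another stopping reason comes first.

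**Working it through.** The plan gives no figure on this point to reproduce. The check compares the rules.

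**1. The rules side by side**

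| Finding on repeat scan | First bullet (unconfirmed) | Confirmed-PD list |
|---|---|---|
| Burden vs nadir | must be below 20% | 20% or more, and at least 5 mm, confirms |
| Non-target disease that caused first PD | must be stable or better | worse confirms |
| New lesion that caused first PD | must be stable or better | worse confirms |
| Additional new lesion | no condition | confirms |

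The second bullet makes any one list item sufficient. The section says burden should take in target and non-target lesions. It does not name new lesions, so the 20% condition does not clearly cover an additional one.

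**2. Counting the patterns**

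The inputs are:
- burden (below 20%; 20% or more with at least 5 mm; 20% or more with under 5 mm): 3 states
- new lesion (not a cause; a cause and not worse; a cause and worse): 3 states
- non-target disease (a cause or not, worse or not): 4 states
- additional new lesion (yes or no): 2 states

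That gives 3 × 3 × 4 × 2 = 72 patterns.

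- Meeting both rules as written: 1 burden state (below 20%) × 2 new-lesion states × 3 non-target states × 1 (additional new lesion present) = 6. Every one contains an additional new lesion.
- Meeting both rules once the bullet excludes additional new lesions: 0.
- Meeting neither rule, before and after that change: 1 burden state (20% or more, under 5 mm) × 2 × 3 × 1 (no additional new lesion) = 6.

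These are counts of rule patterns, not of subjects.

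**3. An example**

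Take burden as the target-lesion sum, with non-target disease unchanged. The values are assumed.

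- Nadir: 60 mm.
- First PD scan: 62 mm with one new lesion; 62/60 − 1 = 3.3%, so the new lesion is the cause.
- Repeat scan: 69 mm, that lesion stable, one additional new lesion; 69/60 − 1 = 15.0% over nadir, and 69/62 − 1 = 11.3% (7 mm) over the first PD scan.

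Bullet: below 20% and cause stable, so PD is unconfirmed and treatment may go on. List: additional new lesion, so PD is confirmed. The exception is closed, because burden has risen since the first PD scan. The comparators differ: the bullet uses nadir and the exception uses the first PD scan.

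**4. Which rule is intended**

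- The second bullet and the section's closing sentence require discontinuation once PD is confirmed.
- Protocol 3.5 lists confirmed progression, with a reference to 6.2.9, as a reason to discontinue.
- Table 6-2 gives continuation under the row "Repeat tumor imaging shows SD, PR, or CR by RECIST (see protocol for details". For confirmed PD it says "Discontinue treatment (exception is possible upon consultation with sponsor".
- The last row of the first time-point table in Appendix 5 rates any new lesion as PD, whatever the target and non-target status.

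All of these point to PD. The bullet is the exception.

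**5. Route to the endpoints**

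SAP 6 uses investigator assessments. Under SAP 6.1 and Table 5, a PD response at the confirmatory visit confirms the first PD. If the investigator records PD, as Appendix 5 directs, nothing changes. If a response such as SD is recorded, Table 5 gives pseudo-PD, which SAP 6.2.1 does not count as definitive PD. PFS and DOR could then move, and later assessments could stay eligible for ORR.

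**6. The 5 mm wording**

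An increase of 20% or more that is under 5 mm requires a nadir below 5/0.20 = 25 mm. With no other finding, it meets neither rule.

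**The case against.** The strongest reply is that the documents already settle the matter. The bullet is permissive and the second bullet is mandatory. A scan that meets both a permission and a specific stop should be stopped, and Protocol 3.5, Table 6-2 and Appendix 5 agree. A site goes wrong only by reading one bullet in isolation. Even then, 6.2.9.1 sets minimum criteria for treating after a first PD finding: no signs or symptoms of progression, no ECOG decline, and no rapid or critical-site progression. These apply under either reading.

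Much of this stands. The intent can be recovered, and the clinical criteria limit the exposure. It does not remove the conflict, for three reasons. The bullet states a classification as well as a permission. The Sponsor exception cannot reconcile the two rules, since it begins only once PD is confirmed. And 6.2.9.1 presents its rules as adaptations of RECIST 1.1, so a site could take the bullet as overriding Appendix 5.

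A reader might infer that PFS, DOR or ORR is biased. The documents do not support that. An effect needs a non-PD response recorded despite a new lesion. Moreover, the SAP supplied covers the follow-up analysis. By its sections 1 and 6, formal testing and the efficacy results in the study report follow a primary-analysis SAP that was not supplied.

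A reader might also infer that when target lesions caused the first PD, a repeat scan below 20% over nadir must be smaller than the first PD scan, leaving the exception open. That holds only if burden means the target sum. The section tells sites to consider non-target lesions too.

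**Conclusion.** The point holds as a drafting error in an operative rule. The first bullet of 6.2.9.1 classes as unconfirmed a scan that the list below it classes as confirmed PD, and the rest of the protocol shows the bullet to be the text at fault. The missing condition on additional new lesions is the only source of overlap: 6 patterns of 72 as written, 0 once it is added.

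The consequence is at site level. Treatment and imaging could continue without the clinical-benefit, no-further-increase and Sponsor-consultation conditions, within the limits of the minimum clinical criteria. This assumes a site that relies on the bullet rather than the list.

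Any effect on endpoints also requires a non-PD response to be recorded at the repeat scan. Its size, its frequency and any difference between arms cannot be stated from these documents. The bullet should be corrected, but the error does not in itself call the efficacy analysis into question.

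**What to change.** Add to the first continuation bullet of 6.2.9.1: *and no additional new lesion(s) since last evaluation*. This matches the list item and removes the overlap. It costs one phrase and needs no new data, visits or analyses.

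Optionally, give the bullet's burden condition the same 5 mm absolute-increase wording as the list, so that a rise of 20% or more but under 5 mm no longer falls outside both rules. This matters only for a nadir below 25 mm.

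The change aligns the bullet with the list, not with all of Appendix 5. Progression of non-target disease that did not cause the first PD would still be rated PD there but would not confirm PD under 6.2.9.1. On that case the bullet and the list already agree, so it is outside this correction.

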6.2.9.2. Tumor Imaging

Contrast-enhanced CT (without contrast if use of contrast is contraindicated) or gadolinium-enhanced MRI of the chest, abdomen, and pelvis will be performed at screening, every 8 weeks during the study and at the EOS visit if one has not been performed within the last 8 weeks. CT is the preferred imaging modality for this study. Tumor burden will be evaluated solely based on radiographic imaging per RECIST v 1.1, with the modifications noted in Section 6.2.9.1. Chest x-ray, ultrasound, endoscopy, laparoscopy, positron-emission tomography, radionuclide scans, or tumor markers will not be considered for response assessment.

For radiographic evaluations, it is recommended that the same method of assessment and the same technique (eg, scan type, scanner, subject position, dose of contrast, injection/scan interval) should be used to characterize each identified and reported lesion at baseline and during study treatment and follow-up. Local site study team reading (investigator assessment with site radiology reading) based on RECIST 1.1 will be used to determine subject eligibility.

Scans taken as part of standard medical practice up to 28 days prior to randomization can be used for Screening as long as they are of diagnostic quality and meet all study requirements. During the treatment phase, scans may be performed at time points other than every 8 weeks as clinically indicated to assess tumor progression.

For subjects who stop study treatment in the absence of disease progression (eg, experienced unexpected toxicity), scans should continue to be collected approximately every 8 weeks until disease progression or initiation of systemic anti-tumor therapy other than the study treatment, whichever is earlier.

All relevant clinical and radiographic information required to make each assessment must be made available for source verification and submission to a central reader. CCI [REDACTED] Disease progression will be determined by the investigator or qualified designee.

Imaging should be continued at protocol-specified intervals until whichever of the following occurs first:

- Initial site-assessed disease progression is confirmed
- The start of new anti-cancer treatment
- Withdrawal of consent
- Death
- The end of the study

